5.3.3.5. PRO data

If there are missing items on the FBISI-18, subscale scores can be prorated. This is done by multiplying the sum of the subscale by the number of items in the subscale, then dividing by the number of items actually answered, as follows:

Prorated subscale score = [Sum of item scores] × [Number of items in subscale] ÷ [Number of items answered]

When there are missing data, prorating by subscale in this way is acceptable if > 50% of the items were answered. The total score is then calculated as the sum of the un-weighted subscale scores. In addition, a total score should only be calculated if all of the component subscales have valid scores.

For the EQ-5D-5L, questions not answered will be considered missing items and will not be

utilized. For EQ-5D-5L, the entire utility score for that cycle is deemed missing if the answer to any one of the 5 dimensions is missing.

6. ANALYSES AND SUMMARIES

Refer to [Section 4](#) for definitions of analysis sets and [Section 5.2](#) for general methodology.

6.1. Primary Endpoint

6.1.1. Overall Survival

6.1.1.1. Primary Analysis

The following analyses will be based on the FAS using the strata assigned at randomization.

Overall survival (OS) is defined as the time from date of randomization to the date of death due to any cause. Patients last known to be alive will be censored at date of last contact.

$$\text{OS (months)} = [\text{date of death or censoring} - \text{date of randomization} + 1] / 30.4375$$

The primary analysis of OS will compare the OS time between the experimental arm and the control arm within each of the co-primary populations, and will be performed using a one-sided stratified log-rank test as described in [Section 5.1](#).

The treatment effect will be estimated using a Cox's Proportional Hazard model stratified by the randomization strata to calculate the hazard ratio. Each stratum will define a separate baseline hazard function (using the 'STRATA' statement in SAS PROC PHREG), ie for the i -th stratum the hazard function is expressed as: $h(i;t) = h(i,0;t) \exp(x\beta)$, where $h(i,0;t)$ defines the baseline hazard function for the i -th stratum and x defines the treatment arm (0=control arm, 1= experimental arm) and β is the unknown regression parameter.

Ties will be handled by replacing the proportional hazards model by the discrete logistic model (Ties=Discrete option in SAS PROC PHREG).

In order to account for the group sequential design in this study, the repeated CI (RCI) method ([Jennison and Turnbull, 2000](#)), will be used to construct the 2-sided RCIs for the hazard ratio at the interim and the final analyses of OS.

In addition, the unadjusted 95% CIs for the hazard ratio will also be reported at the interim and the final analyses for OS.

Kaplan-Meier estimates (product-limit estimates) will be presented by treatment arm together with a summary of associated statistics including the median OS time with two-sided 95% CIs. In particular, the OS rates at 6, 12, 18, 24 and 30 months will be estimated with corresponding 2-sided 95% CIs. The CIs for the median will be calculated according to [Brookmeyer and Crowley \(1982\)](#) and the CIs for the survival function estimates at the time points defined above will be derived using the log-log transformation according to [Kalbfleisch and Prentice \(2002\)](#) (conftype=loglog default option in SAS Proc LIFETEST) with back transformation to a CI on the untransformed scale. The estimate of the standard error will be computed using Greenwood's formula.

Frequency (number and percentage) of patients with an event (death) and censoring reasons will be presented by treatment arm. Reasons for censoring will be summarized according to the categories in Table 7 following the hierarchy shown.

Table 7. OS Censoring Reasons and Hierarchy

Hierarchy	Condition	Censoring Reason
1	No event and [withdrawal of consent date \geq date of randomization OR End of study (EOS) = Patient refused further follow-up]	Withdrawal of consent
2	No event and [lost to follow-up in any disposition page OR data cut-off date – last contact date > 16 weeks]	Lost to follow-up
3	No event and none of the conditions in the prior hierarchy are met	Alive

The OS time or censoring time and the reasons for censoring will also be presented in a patient listing.

Time of Follow-Up for OS

A Kaplan-Meier plot for OS follow-up duration will also be generated to assess the follow-up time in the treatment arms reversing the OS censoring and event indicators. Kaplan-Meier estimates (product-limit estimates) will be presented by treatment arm together with a summary of associated statistics including the median time of follow-up for OS with 2-sided 95% CIs. In particular, the rates 6, 12, 18, 24 and 30 months will be estimated with corresponding 2-sided 95% CIs.

6.2. Secondary Endpoint(s)

6.2.1. Safety Endpoints

Refer to [Section 6.6](#).

6.2.2. Efficacy Endpoints

The following analyses will be based on the FAS by treatment arm unless otherwise specified. Assessment of response will be made using RECIST v1.1. Analyses for tumor-related endpoints will be performed based on BICR assessment and based on Investigator assessment.

Efficacy endpoints defined below will be summarized separately for each of the co-primary populations.

6.2.2.1. Progression Free Survival

Progression-Free Survival (PFS) is defined as the time from the date of randomization to the date of the first documentation of PD or death due to any cause, whichever occurs first.

PFS data will be censored on the date of the last adequate tumor assessment for patients who do not have an event (PD or death), for patients who start a new anti-cancer therapy prior to an event (see Section 5.2.6) or for patients with an event after 2 or more missing tumor assessments. Patients who do not have an adequate baseline tumor assessment or who do not have an adequate post-baseline tumor assessment will be censored on the date of randomization unless death occurred on or before the time of the second planned tumor assessment (ie ≤ 16 weeks after the date of randomization) in which case the death will be considered an event.

In this study antitumor activity will be assessed through radiological tumor assessments conducted at screening, at 8 weeks after randomization, then every 8 (± 3 days) weeks for up to 1 year from randomization, and every 12 weeks (± 3 days) thereafter until PD as assessed by BICR regardless of initiation of subsequent anti-cancer therapy.

The censoring and event date options to be considered for the PFS and DR analysis are presented in Table 8.

$$\text{PFS (months)} = [\text{date of event or censoring} - \text{date of randomization} + 1] / 30.4375$$

Table 8. Outcome and event dates for PFS analyses

Scenario	Date of event/censoring	Outcome
No adequate baseline assessment	Date of randomization ^a	Censored ^a
PD or death - After at most one missing or inadequate post-baseline tumor assessment, OR - ≤ 16 weeks after the date of randomization	Date of PD or death	Event
PD or death - After 2 or more missing or inadequate post-baseline tumor assessments	Date of last adequate tumor assessment ^b documenting no PD before new anti-cancer therapy is given or missed tumor assessments	Censored
No PD and no death	Date of last adequate tumor assessment ^b documenting no PD before new anti-cancer therapy is given or missed tumor assessments	Censored
Treatment discontinuation due to 'Disease progression' without documented progression	Not applicable	Information is ignored. Outcome is derived based on documented progression only.
New anti-cancer therapy given	Date of last adequate tumor assessment ^b documenting no PD before new anti-cancer therapy is given or missed tumor assessments	Censored

^a However if the patient dies ≤ 16 weeks after the date of randomization the death is an event with date on death date

^b If there are no adequate post-baseline assessments prior to PD or death, then the time without adequate

Scenario	Date of event/censoring	Outcome
assessment should be measured from the date of randomization; if the criteria were met the censoring will be on the date of randomization.		

A stratified log-rank test (1-sided) will be used to compare the PFS time based on BICR assessment between the experimental arm and the control arm.

The treatment effect will be estimated using a Cox's Proportional Hazard model stratified by the randomization strata to calculate the hazard ratio. Each stratum will define a separate baseline hazard function (using the 'STRATA' statement in SAS PROC PHREG), ie for the *i*-th stratum the hazard function is expressed as: $h(i;t) = h(i,0;t) \exp(x\beta)$, where $h(i,0;t)$ defines the baseline hazard function for the *i*-th stratum and x defines the treatment arm (0=control arm, 1= experimental arm) and β is the unknown regression parameter.

Ties will be handled by replacing the proportional hazards model by the discrete logistic model (Ties=Discrete option in SAS PROC PHREG).

Kaplan-Meier estimates (product-limit estimates) will be presented by treatment arm together with a summary of associated statistics including the median PFS time with 2-sided 95% CIs. In particular, the PFS rates at 3, 6, 9, 12 and 15 months will be estimated with corresponding 2-sided 95% CIs. The CIs for the median will be calculated according to Brookmeyer and Crowley (1982) and the CIs for the survival function estimates at the time points defined above will be derived using the log-log transformation according to Kalbfleisch and Prentice (2002) (conftype=loglog default option in SAS Proc LIFETEST) with back transformation to a CI on the untransformed scale. The estimate of the standard error will be computed using Greenwood's formula.

Frequency (number and percentage) of patients with each event type (PD or death) and censoring reasons will be presented by treatment arm. Reasons for censoring will be summarized according to the categories in Table 9 following the hierarchy shown.

Table 9. PFS Censoring Reasons and Hierarchy

Hierarchy	Condition	Censoring Reason
1	No adequate baseline assessment	No adequate baseline assessment
2	Start of new anti-cancer therapy	Start of new anti-cancer therapy
3	Event after 2 or more missing or inadequate post-baseline tumor assessments/date of randomization	Event after 2 or more missing assessments ^a
4	No event and [withdrawal of consent date \geq date of randomization OR End of study (EOS)= Patient refused further follow-up]	Withdrawal of consent
5	No event and lost to follow-up in any disposition page	Lost to follow-up
6	No event and [EOS present OR disposition page for any epoch after screening says patient will not continue into any subsequent phase of the study] and no adequate post-baseline tumor assessment	No adequate post-baseline tumor assessment

7	No event and none of the conditions in the prior hierarchy are met	Ongoing without an event
---	--	--------------------------

^a 2 or more missing or inadequate post-baseline tumor assessments.

The PFS time or censoring time and the reasons for censoring will also be presented in a patient listing.

Time of Follow-Up for PFS

A plot will be generated to compare planned and actual relative day of tumor assessments by treatment arm. A Kaplan-Meier plot for PFS follow-up duration will also be generated to assess the follow-up time in the treatment arms reversing the PFS censoring and event indicators. Kaplan-Meier estimates (product-limit estimates) will be presented by treatment arm together with a summary of associated statistics including the median time of follow-up for PFS with 2-sided 95% CIs. In particular, the rates at 3, 6, 9, 12 and 15 months will be estimated with corresponding 2-sided 95% CIs.

BICR vs Investigator Assessment

A summary of the BICR assessment versus investigator assessment will be provided including numbers of concordant and discordant assessments as well as the number of cases where PFS event was assessed at different timepoints based on BICR and investigator assessments.

Table 10 outlines the possible outcomes by investigator and BICR ([Amit et al, 2011](#)).

Table 10. Possible Outcomes for Investigator vs BICR

		BICR	
		Event	No Event
Investigator	Event	a = a1 + a2 + a3	b
	No Event	c	d

a1: number of agreements on timing and occurrence of event;
 a2: number of times agreement on event but INV declares event later than BICR;
 a3: number of times agreement on event but INV declares event earlier than BICR;
 N= a+b+c+d.

The timing agreement of event is defined as a window of ± 7 days

The following measure of discordance will be calculated for each treatment arm:

- Total Event Discrepancy Rate: $(b+c) / N$
- Early Discrepancy Rate (EDR): $(a3+b) / (a+b)$
- Late Discrepancy Rate (LDR): $(a2+c) / (a2+a3+b+c)$
- Overall Discrepancy Rate: $(a2+a3+b+c) / N$

The EDR represents the positive predictive value of investigator assessment and quantifies the frequency with which the investigator declares PFS event earlier than BICR within each treatment arm as a proportion of the total number of investigator assessed events.

The LDR quantifies the frequency with which the investigator declares PFS event later than BICR as a proportion of the total number of discrepancies within the treatment arm.

Discordance metrics are calculated for each treatment arm and, for each metric, the difference in discordance between the experimental and control arms is used to evaluate potential bias. If the discordance is similar across the treatment arms, then this suggests the absence of evaluation bias favoring a particular treatment arm. A negative differential discordance for EDR and/or a positive differential discordance for LDR may be indicative of investigator evaluation bias in favor of the experimental arm (Amit et al, 2011).

6.2.2.2. Sensitivity analyses for overall survival

The following sensitivity analyses will be performed to explore the robustness of the primary analysis results for OS. These analyses are regarded as purely exploratory. The sensitivity analyses will repeat the primary analysis (p-value, HR and 95% CIs) described in Section 6.1.1.1 with the modifications below:

- PP analysis set
- unstratified

Methods for evaluating the validity of model assumptions

The proportional hazards assumption will be checked visually by plotting $\log(-\log(\text{OS}))$ versus $\log(\text{time})$ within each randomization stratum.

Schoenfeld residuals for the stratified Cox proportional regression model will be plotted to investigate graphically violations from the proportional hazards (PH) assumption; a non-zero slope is evidence of departure from PH. The PH assumption will be formally tested using Schoenfeld's residual test (Schoenfeld, 1980; Therneau and Grambsch, 2000). Large departures from PH will be evidenced by a p-value <0.05 .

If these show large departures from proportional hazards, then OS assessment will also be analyzed based on restricted mean survival time (RMST) differences (Zhang, 2013).

Restricted Mean Survival Time (RMST)

The hazard ratio estimate from the Cox proportional hazard model is routinely used to empirically quantify the between-arm difference under the assumption that the ratio of the two hazard functions is constant over time. When this assumption is plausible, such a ratio estimate may capture the relative difference between two survival curves. However, the clinical meaning of such a ratio estimate is difficult, if not impossible, to interpret when the underlying PH assumption is violated (ie, the hazard ratio is not constant over time).

The RMST is a robust and clinically interpretable summary measure of the survival time distribution. Unlike median survival time, it is estimable even under heavy censoring. There is a considerable body of methodological research (eg, Royston and Parmar, 2011; Uno, Wei, et al, 2014; Zhang, 2013) about the use of RMST to estimate treatment effects as an alternative to the hazard ratio approach.

The RMST methodology is applicable independently of the PH assumption and can be used, at a minimum, as a sensitivity analysis to explore the robustness of the primary analysis results. However, when large departures from the PH assumption are observed, the log-rank test is underpowered to detect differences between the survival distributions for the treatment arms, and a test of the difference between the RMST for the experimental arm and the control arm may be more appropriate to determine superiority of the experimental arm compared to the control arm with respect to the time-to-event endpoint.

In particular, as it pertains to the **cut-off point (τ)** to evaluate the RMST, it is noted that the cut-off point should not exceed the minimum of the largest observed time for both treatment arms so that the RMST of all treatment arms being evaluated can be adequately estimated and comparison between treatments is feasible; τ should be clinically meaningful and closer to the end of the study follow-up so that the majority of survival outcomes will be covered by the time interval. The RMST up to time τ can then be interpreted as the expected survival time restricted to the common follow-up time τ among all patients. The selection of τ should ensure that the RMST evaluation will not go beyond the maximum time point where the evaluation can be performed while also taking into account a large period of time that is expected to provide a meaningful assessment of treatment effect. To avoid arbitrary selection of the common cut-off τ for both treatment arms, three sets of analyses will be performed:

- τ_1 = minimum of (largest observed OS time for the experimental arm, largest observed OS time for the control arm).
- τ_2 = minimum of (largest OS event time for the experimental arm, largest OS event time for the control arm).
- τ_3 = midpoint between τ_1 and τ_2 .

The treatment effect between the experimental arm and the control arm will be assessed based on the difference in RMST. The associated 95% CI for the difference in means and 1-sided p-value will be generated.

Exploratory analyses to investigate the impact of potential prognostic or effect modifying (predictive) factors

See subgroups as defined in Section 6.4.

Multivariable Cox regression analysis will be carried out to assess and adjust the treatment effect for relevant baseline factors of potential prognostic impact. A stepwise selection procedure will serve to identify explanatory variables of potential prognostic values

additional to the randomization strata which will be included in all models during the selection procedure. The Cox's Proportional Hazard model is defined as:

$$h(t) = h(0;t) e^{Xb}$$

where $h(0;t)$ defines the baseline hazard function and X defines the vector of explanatory variables and b the unknown vector of regression parameters.

In the stepwise selection procedure, variables are entered into and removed from the model in such a way that each forward selection step can be followed by one or more backward elimination steps. The stepwise selection process terminates if no further variable can be added to the model or if the variable just entered into the model is the only variable removed in the subsequent backward elimination. The level of significance for an explanatory variable to enter the model is set to 0.15 (p-value of Score test) and the significance level for removing it is set to 0.40 (p-value of Wald test). This analysis will be performed using the stepwise selection method in SAS (Proc PHREG). Once this procedure stops, the factor 'treatment arm' will be added to the last selected model in order to evaluate the effect of treatment on OS time when adjusted for the selected explanatory variables. The hazard ratios of all selected explanatory variables and of treatment effects will be reported including 2-sided 95% CIs. No interactions will be considered. Post-baseline factors will not be considered for the model.

6.2.2.3. Objective response and tumor shrinkage

Best overall response (BOR) will be assessed based on reported overall lesion responses at different evaluation time points from the date of randomization until the first documentation of PD, according to the following rules. Only tumor assessments performed on or before the start date of any further anti-cancer therapies will be considered in the assessment of BOR. Clinical deterioration will not be considered as documentation of disease progression.

BOR Based on Confirmed Responses:

- CR = at least two determinations of CR at least 4 weeks apart and before first documentation of PD.
- PR = at least two determinations of PR or better (PR followed by PR or PR followed by CR) at least 4 weeks apart and before first documentation of PD (and not qualifying for a CR).
- SD (applicable only to patients with measurable disease at baseline) = at least one SD assessment (or better) ≥ 6 weeks after the date of randomization and before first documentation of PD (and not qualifying for CR or PR).
- Non-CR/non-PD (applicable only to patients with non-measurable disease at baseline) = at least one non-CR/non-PD assessment (or better) ≥ 6 weeks after the date of randomization and before first documentation of PD (and not qualifying for CR or PR).
- PD = first documentation of PD ≤ 12 weeks after the date of randomization (and not qualifying for CR, PR, SD or non-CR/non-PD).

- NE: all other cases.

An objective status of PR or SD cannot follow one of CR. SD can follow PR only in the rare case that tumor increases by less than 20% from the nadir, but enough that a previously documented 30% decrease from baseline no longer holds. If this occurs, the sequence PR-SD-PR is considered a confirmed PR. A sequence of PR – SD – SD – PD would be a best response of SD if the window for SD definition has been met.

Objective Response (OR) is defined as confirmed BOR of CR or PR according to RECIST v1.1.

Patients who do not have a post-baseline radiographic tumor assessment due to early progression, who receive anti-tumor therapies other than the study treatments prior to reaching a CR or PR, or who die, progress, or drop out for any reason prior to reaching a CR or PR will be counted as non-responders in the assessment of OR. Each patient will have an objective response status (0: no OR; 1: OR). OR rate (ORR) is the proportion of patients with OR in the analysis set.

ORR by treatment arm will be calculated along with the 2-sided 95% CI using the [Clopper-Pearson](#) method (exact CI for a binomial proportion as computed by default by the FREQ procedure using the EXACT option).

In addition, the frequency (number and percentage) of patients with a confirmed BOR of CR, PR, SD, non-CR/non-PD (applicable only to patients with non-measurable disease at baseline), PD, and NE will be tabulated. Patients with confirmed BOR of NE will be summarized by reason for having NE status. The following reasons will be used:

- No baseline assessment
- No evidence of disease at baseline
- No post-baseline assessments due to death
- No post-baseline assessments due to other reasons
- All post-baseline assessments have overall response NE
- New anti-cancer therapy started before first post-baseline assessment
- SD of insufficient duration (<6 weeks after the date of randomization without further evaluable tumor assessments)
- PD too late (>12 weeks after the date of randomization)

Special and rare cases where BOR is NE due to both SD of insufficient duration and late PD, will be classified as ‘SD too early’ (ie, SD of insufficient duration).

The association of study treatment and OR will be tested by the General Association Statistic of the [Cochran-Mantel-Haenszel test \(CMH\)](#) with the randomization strata taken into account. The null hypothesis of no association in any of the randomization strata is tested

against the alternative, which specifies that there is an association between study treatment and tumor response at least in one randomization stratum. The CMH test will be performed at 1-sided alpha level of 0.025.

The stratified odds ratio in terms of OR will also be estimated along with its 95% CI to compare study treatments. The odds ratio is defined as the odds of OR with experimental treatment divided by the odds of OR with control treatment. The Breslow-Day test will be used to check the homogeneity of the odds ratio across the randomization strata. It tests the null hypothesis that odds ratios in all strata are equal against the alternative hypothesis that at least in one stratum the odds ratio is different.

In case the null hypothesis of homogeneity of odds ratios across strata is not rejected at the 2-sided alpha level of 0.05, the common odds ratio will be determined using the Mantel-Haenszel estimate (by the FREQ procedure using CMH option in SAS); if the null hypothesis of homogeneity of odds ratio across all strata is rejected, the odds ratio per stratum will be calculated with the corresponding exact CI.

BICR vs Investigator Assessment:

Table 11 outlines the possible BOR outcomes by investigator and BICR.

Table 11. Possible BOR Outcomes for Investigator vs BICR

BOR		BICR Assessment					
		CR	PR	SD	Non-CR/ non-PD	PD	NE
Investigator Assessment	CR	n ₁₁	n ₁₂	n ₁₃	n ₁₄	n ₁₅	n ₁₆
	PR	n ₂₁	n ₂₂	n ₂₃	n ₂₄	n ₂₅	n ₂₆
	SD	n ₃₁	n ₃₂	n ₃₃	n ₃₄	n ₃₅	n ₃₆
	Non-CR/ non-PD	n ₄₁	n ₄₂	n ₄₃	n ₄₄	n ₄₅	n ₄₆
	PD	n ₅₁	n ₅₂	n ₅₃	n ₅₄	n ₅₅	n ₅₆
	NE	n ₆₁	n ₆₂	n ₆₃	n ₆₄	n ₆₅	n ₆₆

$\sum_{i=1}^6(n_{ii})$ is the number of agreements on BOR between BICR and Investigator

$\sum_{i,j=1}^6(n_{ij})$ for $i \neq j$ is the number of disagreements on BOR between BICR and Investigator

$N = \sum_{i,j=1}^6(n_{ij})$

The following measures of concordance will be calculated for each treatment arm:

- Concordance rate for BOR = $\sum_{i=1}^6(n_{ii}) / N$
- Concordance rate for response = $[\sum_{i,j=1}^2(n_{ij}) + \sum_{i,j=3}^6(n_{ij})] / N$

Concordance rates are calculated for each treatment arm and, for each metric, the difference in concordance between the experimental and control arms are used to evaluate potential bias. If the concordance is similar across the treatment arms, then this suggests the absence of evaluation bias favoring a particular treatment arm.

Tumor Shrinkage from Baseline:

Tumor shrinkage will be summarized as the percent change from baseline in target lesions (sum of longest diameter for non-nodal lesion and short axis for nodal lesion) per time point. It will be derived as:

- $((\text{Sum of target lesions at week XX} - \text{sum of target lesions at baseline}) / \text{sum of target lesions at baseline}) \times 100$

The maximum reduction in target lesions from baseline will be derived across all the post-baseline assessments until documented disease progression, excluding assessments after start of subsequent anti-cancer therapy, as:

- Minimum of $((\text{sum of target lesions at week XX} - \text{sum of target lesions at baseline}) / \text{sum of target lesions at baseline}) \times 100$

A waterfall plot of maximum percent reduction in the sum of longest diameter for non-nodal lesions and short axis for nodal lesions from baseline will be created by treatment arm. These plots will display the best percentage change from baseline in the sum of the diameter of all target lesions for each patient with measurable disease at baseline and at least one post-baseline assessment.

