3.4.2. Baseline Characteristics

Randomization is stratified by the following, as recorded in the Interactive Response Technology (IRT) system:

- Best response to first-line chemotherapy (CR or PR vs. SD)
- Metastatic disease site (visceral vs. non-visceral) at the time of initiating first-line chemotherapy. The ‘non-visceral’ stratum includes patients with locally-advanced disease as well as patients with only non-visceral disease.

The primary analyses of OS will be stratified by these randomization stratification factors.

Other baseline characteristics (including demographics, physical measurements, disease history and prior anti-cancer therapies) are described in [Section 6.5.1](#). These baseline characteristics are not planned to be included as stratification variables or covariates in statistical models unless otherwise specified in [Section 6](#).

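### The objective-response test joins a non-directional CMH statistic and alternative to a one-sided 0.025 level, and the SAP does not say how the one-sided p-value is obtained

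*SAP*

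**What the plan says.** SAP Section 6.2.2.3 specifies the test in three steps.

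- Statistic: "The association of study treatment and OR will be tested by the General Association Statistic of the" Cochran-Mantel-Haenszel (CMH) procedure, stratified by the randomization strata.
- Alternative: "there is an association between study treatment and tumor response at least in one randomization stratum". No arm is named as the better one.
- Level: "The CMH test will be performed at 1-sided alpha level of 0.025".

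The same section codes response as a 0/1 status per patient and gives response rates by arm with exact confidence intervals. It adds an effect measure: "The stratified odds ratio in terms of OR will also be estimated along with its 95% CI to compare study treatments", with Arm A in the numerator. If the Breslow-Day test rejects homogeneity, the common odds ratio is replaced by one odds ratio per stratum.

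SAP Section 6.2.2 applies the tumor endpoints to BICR and to investigator assessment, and to each co-primary population, so the wording governs four comparisons. Protocol Section 9.3.2 plans only arm-level rates with exact intervals for objective response. The alpha split and the stopping boundaries in SAP Section 5.1 concern overall survival only.

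**The concern.** A chi-square statistic on 1 degree of freedom is the square of a signed score. Squaring discards the sign, so large values arise equally from more responses and from fewer responses on avelumab. The stated alternative has the same property. A one-sided level attached to such a test is undefined until a rule restores direction. The section names no signed root, no halved p-value and no check of the odds ratio.

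Two programmers could therefore follow the same text and use rejection regions whose one-sided levels differ by a factor of two. Under one of these regions, a significant result would not by itself show that avelumab is better, and the test could disagree with the confidence interval printed beside it.

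The SAP is explicit about direction elsewhere. The survival hypotheses in Section 5.1.1 are written as a hazard ratio below 1, Table 5 gives signed z boundaries, and the Breslow-Day test is given a two-sided level. Objective response is the exception.

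**Working it through.** **Inputs.** Binary response and two arms (SAP 6.2.2.3); two stratification factors with two levels each, hence four strata (SAP 3.4.2); level 0.025, one-sided (SAP 6.2.2.3); about 668 patients randomized 1:1, at least 334 of them PD-L1-positive (SAP 2.2).

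**Form of the statistic.** Let stratum k have responders a and non-responders b in Arm A, responders c and non-responders d in Arm B, and total T. The score is Z = Σ(a − E[a]) / √ΣVar(a), and the General Association statistic is Q = Z². Also a − E[a] = a − (a+b)(a+c)/T = (ad − bc)/T. So Z is positive exactly when Σ(ad/T) exceeds Σ(bc/T), which is exactly when the Mantel-Haenszel odds ratio exceeds 1.

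**Signed root: reproduces the stated level.** Reject if Z > 1.960, that is, Q > 3.841 with an odds ratio above 1. The level is P(Z > 1.960) = 0.0250, with no rejection for harm.

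**Chi-square p-value compared directly with 0.025.** Reject if Q > 5.024, that is, |Z| > 2.241. The level is P(Z > 2.241) = 0.0125 for benefit and the same for harm, 0.025 in total.

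**Check by simulation.** Four strata, 400,000 replicates. Stratum shares of 40, 30, 18 and 12% and null response rates of about 5%, 7.8% and 15% are assumptions.

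| N | Signed root | Direct, favouring Arm A | Direct, favouring Arm B |
|---|---|---|---|
| 668 | 0.0249–0.0251 | 0.0122–0.0127 | 0.0121–0.0124 |
| 334 | 0.0245–0.0248 | 0.0112–0.0121 | 0.0111–0.0122 |

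**Agreement with the confidence interval.** A 95% interval for the odds ratio excludes 1, up to approximation, when Q > 3.841 (p < 0.05). Under the direct comparison, results with Q between 3.841 and 5.024 (p between 0.025 and 0.05) would be called non-significant while the interval excludes 1.

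**Cost in power under the direct comparison (illustrative only).** The documents state no power for objective response.

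- Assume 80% power at one-sided 0.025. At the stricter cut-off, power is Φ(1.960 + 0.842 − 2.241) = Φ(0.561) = 0.71.
- Take response rates of 13.8% and 7.8%, from the maintenance lapatinib trial described in protocol Section 1.2.3.1; they are not planning values for this trial. Unstratified power is Φ[(0.06 − z·SE₀)/SE₁], where SE₀ = √(2 × 0.108 × 0.892/n), SE₁ = √((0.138 × 0.862 + 0.078 × 0.922)/n) and n is patients per arm.
  - n = 334: SE₀ = 0.02402, SE₁ = 0.02391; power 0.71 at z = 1.960 and 0.60 at z = 2.241.
  - n = 167: SE₀ = 0.03397, SE₁ = 0.03381; power 0.42 and 0.32.

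**The case against.** The strongest reply is that the SAP says one-sided, and for a 1-df statistic the ordinary way to honour that is the signed root, which gives exactly 0.025. The SAP's one-sided log-rank tests support this: a log-rank test is also often reported as a chi-square, yet for survival the SAP works with signed z values. Direction would in any case be visible from the arm-level rates and the odds ratio, so a result favouring best supportive care could hardly be presented as benefit.

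Much of this stands. A reader might infer that the true one-sided level is 0.0125 and that the stated error rate is simply false. The documents do not support that: they nowhere say that the chi-square p-value is set directly against 0.025, so 0.0125 is the result of one of two implementations left open. Nor is there any inflation of error in favour of avelumab, because the direct comparison is conservative in that direction.

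Two things remain. The usage in other sections is context, not a rule for this test, and the alternative written here is non-directional. The odds ratio is reported alongside the test but is not part of the decision rule; if homogeneity is rejected, the plan gives no common odds ratio to accompany the overall test.

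**Conclusion.** The point holds as an internal mismatch: wrong as written, and minor. The statistic and the alternative define a two-directional test, and the one-sided 0.025 attached to it is obtained only through a step the SAP does not state. The one-sided level is 0.025 with the signed root and 0.0125 with direct comparison of the chi-square p-value; the text does not settle which applies.

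Under the direct comparison the loss is about 9 to 11 percentage points of power in the illustrations. Those figures rest on an assumed 80% starting power, or on response rates borrowed from another trial. The levels rest only on the large-sample normal approximation, which the simulation supports under its assumed strata and response rates. Objective response is a secondary endpoint outside the survival alpha scheme, so the primary conclusion does not depend on this.

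**What to change.** Amend SAP Section 6.2.2.3 in one of two equivalent ways.

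1. State the alternative as a common odds ratio (Arm A over Arm B) greater than 1, and take a one-sided p-value from the signed square root of the CMH statistic at 0.025 (Z > 1.96). The sign comes from the summed observed-minus-expected responders in Arm A, so it is available even when the odds ratios are reported by stratum.
2. Call the test two-sided at 0.05 using the chi-square p-value, and require the Mantel-Haenszel odds ratio to exceed 1 before concluding benefit. Retain that odds ratio for direction even if homogeneity is rejected.

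Because Z > 0 exactly when the Mantel-Haenszel odds ratio exceeds 1, both give the same rejection region for benefit. Either makes the test match its stated level and, up to approximation, the planned 95% interval. The cost is about one sentence; the same procedure output serves, with no new data or analysis.
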